**MRI and Biological Markers of Acute E-Cigarette Exposure in Smokers and Vapers**

**NCT 03479203**

**September 15, 2017**

[figure not shown]
To determine the acute effects of e-cig aerosol inhalation we will quantify surrogate markers of EDF at the micro- and macro-vascular level before and after a nicotine-free e-cig aerosol in healthy subjects without history of cardiovascular disease.

In order to isolate and assess the acute effects of inhaled aerosol on surrogate MRI markers of EDF (endothelial dysfunction), nicotine-naïve (i.e. non-smokers) will undergo an e-cig aerosol inhalation challenge using a commercially available, disposable, non-flavored nicotine-free e-cig (ECO series, epuffer.com).

All MR procedures will be performed on a 3T Siemens TIM Trio imager (Siemens Medical Solutions) using standard RF coils (8-channel extremity coil for cuff paradigm studies at the location of the femoro-popliteal artery and vein, and a combination of two body matrix and 12-channel head coils for PWV (pulse wave velocity) of the aorta and neurovascular reactivity in the superior sagittal sinus (SSS) in conjunction with the custom-designed pulse sequences. Subjects will be asked to fast for eight hours, have abstained from taking vasoactive medications (including over-the-counter medications) as well as vigorous physical activity. Each visit will comprise two blood draws and two qMRI (quantitative magnetic resonance imaging) examinations, one before and one after an e-cig challenge to assess the changes in the functional and mechanical metrics described in the previous section. The e-cig challenge will consist of 16 two-second-long puffs (equivalent to smoking one conventional cigarette). Smoking will be directly supervised to prevent superficial smoking or hyperventilation by the study subjects. The challenge will last approximately 20 minutes. A second blood draw will be taken six hours after the e-cig challenge. From the blood samples collected, inflammatory biomarkers will be assessed.

Blood will be drawn from the antecubital vein of the subject's left or right arm. At least 2 mL of plasma will be isolated and kept frozen after centrifuging blood for 15 min.

The qMRI protocol will consist of three parts (cuff paradigm, PWV and breath-hold index). The patient set-up for PWV and breath-hold index (BHI) will be combined, i.e. the patient will enter the scanner head-first, supine, with head and body matrix coils in place. Vascular reactivity in the femoral artery and vein will be quantified first. After the cuff-induced hyperemia portion of the protocol the patient will be prepared for the second part designed to measure aortic PWV and BHI.

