### Data and Statistical Analysis

The fractional changes in functional and mechanical qMRI parameters between pre- and post-nicotine challenge will be determined. For each parameter paired two-tailed t-tests will be performed with  $p < 0.05$  indicating statistical significance. The data will allow us to determine which of the qMRI metrics (peripheral vascular reactivity, central arterial stiffness or neurovascular reactivity), are most sensitive to e-cig aerosol inhalation. We will also further conduct multivariate regression analysis on the within-subject changes controlling for other subject-specific covariates.

To quantify the changes in the levels of inflammatory biomarkers in serum collected from study participants before and after e-cigarette aerosol exposure and compare these metrics with qMRI-derived biomarkers.

Blood drawn from the antecubital vein by a phlebotomist from study participants will be collected into tubes containing clot activator. Serum will be separated within 30 minutes by centrifugation and stored at  $-70^{\circ}\text{C}$  prior to analysis. Inflammatory biomarkers will be detected via enzyme-linked immunosorbent assay (ELISA) techniques from blood draws #1 and 2. MCP-1 and MIP-1 concentrations will be measured using commercially available ELISA kits (R&D Systems, Abingdon, UK); sICAM, sRAGE, IFN- $\gamma$  and TNF- $\alpha$  with RayBiotech kits

(RayBiotech, Inc., Norcross, GA 30092); HMGB1 will be assayed by ELISA kits supplied by IBL International (IBL GmbH).

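### Because the cuff study always precedes PWV and BHI after the aerosol, the data cannot tell whether peripheral reactivity is more or less sensitive than the other two metrics or was only measured sooner

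*Combined protocol and SAP*

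**What the plan says.** The study description under the title provides, at each visit, "two qMRI (quantitative magnetic resonance imaging) examinations, one before and one after an e-cig challenge". On the exposure it says "The challenge will last approximately 20 minutes". It gives no interval from the last puff to the start of the second examination and no duration for any part of the scan.

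The qMRI protocol paragraph that follows sets the order. "Vascular reactivity in the femoral artery and vein will be quantified first". Then: "After the cuff-induced hyperemia portion of the protocol the patient will be prepared for the second part designed to measure aortic PWV and BHI". The two parts use different equipment. The study description lists an "8-channel extremity coil for cuff paradigm studies at the location of the femoro-popliteal artery and vein", whereas the second part uses head and body matrix coils with the subject head-first. Within the second part, "The patient set-up for PWV and breath-hold index (BHI) will be combined"; which of the two comes first is not stated outright.

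Data and Statistical Analysis specifies a paired two-tailed t-test for each parameter. It then says the data will determine "which of the qMRI metrics (peripheral vascular reactivity, central arterial stiffness or neurovascular reactivity), are most sensitive to e-cig aerosol inhalation". The planned regression on within-subject changes adjusts for subject-specific covariates; time since exposure is not named among them.

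**The concern.** The study concerns the acute effect of one short exposure, so the response may change while the subject is in the scanner. Each metric is seen once after the challenge at a visit. Peripheral reactivity always comes from the earlier part and the other two always from the later part. A difference in observed change between peripheral reactivity and PWV or BHI could therefore come from the vascular territory, from the delay, or from both.

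At stake is the only between-territory conclusion that Data and Statistical Analysis announces. Neither a larger sample nor an agreed ranking criterion with confidence intervals would repair it, because either would still rank the metric together with its delay.

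**Working it through.** **What the design identifies.** The documents state no sample size, effect size or timing, so there is no figure of the plan to reproduce. Write the expected post-minus-pre change of a metric, in standardised units, as S × r(t), where S is the sensitivity of interest and r(t) is the share of the response present t minutes after the last puff. The cuff metric is observed at t1 and PWV/BHI at t2, with t2 > t1 in every subject. The ratio of the two changes is then

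(S_cuff / S_other) × (r(t1) / r(t2)).

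Only the product is observed. The pre-challenge scan runs in the same order but follows no exposure, so subtracting it removes baseline differences and leaves r(t1)/r(t2) in place. The factor equals 1 only if the response is flat between t1 and t2, and a single post-challenge examination in fixed order gives little means of showing that.

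**Illustration; every input is an assumption.** Take two metrics with equal S and the same time course.

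*Decaying response.* The later metric retains f = 0.5^(gap / half-life). Suppose metrics are ranked by mean standardised change, with n = 30, standardised change 0.6 and correlation 0.5 between metrics. The probability that the earlier one ranks first is approximately

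Φ( 0.6 × (1 − f) / √(2 × (1 − 0.5) / 30) ), with denominator √(1/30) = 0.183.

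Example, gap 30 min and half-life 60 min: f = 0.707; 0.6 × 0.293 = 0.176; 0.176 / 0.183 = 0.96; Φ = 0.83.

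| Gap | Half-life 30 min | 60 min | 120 min |
|---|---|---|---|
| 15 min | f 0.71; 83% | f 0.84; 70% | f 0.92; 61% |
| 30 min | f 0.50; 95% | f 0.71; 83% | f 0.84; 70% |
| 45 min | f 0.35; 98% | f 0.59; 91% | f 0.77; 77% |

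With no time effect the figure would be 50%. The apparent ratio of earlier to later change, 1/f, runs from 1.09 (gap 15, half-life 120) to 2.8 (gap 45, half-life 30).

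*Power of each paired test.* From the noncentral t with n = 30 and two-sided 0.05, power is 0.89 at a standardised change of 0.6 and 0.61 at 0.6 × 0.707 = 0.42. Equal metrics could therefore differ in whether they reach significance.

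*Rising response.* If r(t) = 1 − 2^(−t/h), the later-to-earlier ratio is [1 − 2^(−(t1+gap)/h)] / [1 − 2^(−t1/h)]. With t1 = 20, gap 30 and h = 30 min this is 0.685 / 0.370 = 1.85. Over t1 of 10 to 20 min, gap 15 to 45 min and h of 15 to 60 min it runs from 1.33 (0.802 / 0.603, at t1 = 20, gap 15, h = 15) to 4.31 (0.470 / 0.109, at t1 = 10, gap 45, h = 60). The later metric would then be favoured.

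**The case against.** The strongest defence is that the tests actually specified are separate paired tests for each parameter, and the fixed order does not bias them: each validly estimates the change at that metric's own delay. No between-metric test is planned, and sensitivity could be read operationally as responsiveness under this scan protocol, with the delay as part of the protocol. The first part stands in full. The operational reading is possible, but the plan does not state it, and the sentence names vascular territories.

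A fixed order also has merit. Cuff-induced hyperemia and breath-holding both provoke the vasculature, and a constant order holds any carry-over the same before and after the challenge. Alternating the order could introduce an order-by-exposure effect that one order term need not absorb. This stands, and it is why counterbalancing is not the main recommendation.

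Four stronger readings may tempt a reader:

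- *The ranking is biased in a known direction.* The documents give no delay, block length or time course. The bias could favour either side or be nil.
- *All three metrics are separated by delay.* PWV and BHI share one set-up and their order is only implied by the listing, so that comparison is much less affected.
- *No analysis could ever help.* Minutes since the last puff may vary between subjects, and a within-metric slope on delay might then be estimated. It would be imprecise and would rest partly on extrapolation, but time stamps are not useless.
- *The 83% figure describes this trial.* It is one cell of an assumed grid. The mildest cell gives 61%, and the same formula with a gap of 15 min and a half-life of 240 min gives about 56% (f = 0.958). A common time course across territories is also an assumption.

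**Conclusion.** The point holds as a limit on one conclusion. For peripheral reactivity against PWV or BHI, scan order and time since exposure go together in every subject, and nothing in the plan separates them. The sentence on relative sensitivity therefore claims more than the design can deliver if the response changes during the examination.

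This is a failure of identification; bias has not been demonstrated. The illustrative size depends wholly on the assumed sample size, effect, correlation, gap and time course. The documents allow no estimate for this trial. The point merits correction before analysis but does not call the per-metric results into question.

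**What to change.** 1. Take the minutes from last puff to each acquisition from the scanner time stamps, which requires noting the time of the last puff. Report each metric's change together with the distribution of its delay.
2. In Data and Statistical Analysis, replace the sentence beginning "The data will allow us to determine which of the qMRI metrics" with wording such as: *Changes in each qMRI metric will be reported at that metric's own delay after exposure. Comparisons between the cuff metric and PWV or BHI are descriptive, conditional on the fixed scan order and delay, and are not a ranking of vascular sensitivity.*

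The cost is one recorded time per challenge and one sentence, with no extra scan or subject. The downside is a more limited between-territory conclusion.

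Optional: if a ranking matters to the sponsor, alternate the two set-ups between subjects by a fixed list, keep the same order before and after the challenge within a subject, and include order in the regression already planned. This would break the link between metric and delay, but it may add variance and order-by-exposure carry-over. With no stated sample size, that price cannot be judged from the documents.

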### Data and Statistical Analysis

The fractional changes in functional and mechanical qMRI parameters between pre- and post-nicotine challenge will be determined. For each parameter paired two-tailed t-tests will be performed with  $p < 0.05$  indicating statistical significance. The data will allow us to determine which of the qMRI metrics (peripheral vascular reactivity, central arterial stiffness or neurovascular reactivity), are most sensitive to e-cig aerosol inhalation. We will also further conduct multivariate regression analysis on the within-subject changes controlling for other subject-specific covariates.

To quantify the changes in the levels of inflammatory biomarkers in serum collected from study participants before and after e-cigarette aerosol exposure and compare these metrics with qMRI-derived biomarkers.

Blood drawn from the antecubital vein by a phlebotomist from study participants will be collected into tubes containing clot activator. Serum will be separated within 30 minutes by centrifugation and stored at  $-70^{\circ}\text{C}$  prior to analysis. Inflammatory biomarkers will be detected via enzyme-linked immunosorbent assay (ELISA) techniques from blood draws #1 and 2. MCP-1 and MIP-1 concentrations will be measured using commercially available ELISA kits (R&D Systems, Abingdon, UK); sICAM, sRAGE, IFN- $\gamma$  and TNF- $\alpha$  with RayBiotech kits

(RayBiotech, Inc., Norcross, GA 30092); HMGB1 will be assayed by ELISA kits supplied by IBL International (IBL GmbH).

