### Analyses

Descriptive statistics will initially be performed to determine the characteristics of the various distributions and to identify outliers by displaying the data in the form of box and whisker plots and by computing means and standard deviations. Acute changes from baseline (blood draws pre- and post e-cig aerosol challenge) will be evaluated by paired t-tests for each of the variables listed above. To compare the qMRI metrics with inflammatory indices, Spearman correlations will be performed. We expect moderate inter-modality correlations ( $R^2 \sim 0.5$ ) for individual qMRI measures. We then use linear regression to create a classification model using the eight qMRI indices jointly. We expect  $R^2 > 80\%$ , substantially greater than each individual parameter alone, indicating that inhaled e-cig aerosol promotes *systemic EDF*.

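### Does expressing qMRI change as a fraction bias the planned tests or the choice of the most sensitive metric?

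*Combined protocol and SAP*

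**What the plan says.** Under Data and Statistical Analysis the plan first gives the change measure: "The fractional changes in functional and mechanical qMRI parameters between pre- and post-nicotine challenge will be determined". It then names the test, "For each parameter paired two-tailed t-tests will be performed", with a 0.05 threshold for each. The stated aim follows: "The data will allow us to determine which of the qMRI metrics", completed by "peripheral vascular reactivity, central arterial stiffness or neurovascular reactivity), are most sensitive to e-cig aerosol inhalation". A regression is added as a further step, described as "multivariate regression analysis on the within-subject changes controlling for other subject-specific covariates".

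The opening description of procedures provides for "two qMRI (quantitative magnetic resonance imaging) examinations, one before and one after an e-cig challenge", so each subject contributes a single baseline value per metric.

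For the blood markers, the Analyses section begins "Descriptive statistics will initially be performed to determine the characteristics of the various distributions and to identify outliers" and says that changes from baseline "will be evaluated by paired t-tests for each of the variables listed above".

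Three things are left unstated: the scale on which the qMRI t-test is run, whether fractional change is formed per subject or from group means, and the statistic that decides which metric is most sensitive. The documents give no sample size, standard deviation, repeatability figure or expected size of change.

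**The concern.** Fractional change is the only unit-free measure of change that the plan names for qMRI. The metrics have different units, so a reader may suppose that individual fractions will be averaged, tested and ranked. Each fraction would have one noisy baseline exam as its denominator. Dividing by a noisy quantity inflates the average, so rises would look larger and falls smaller, and more so for noisier metrics.

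Two results would then be at risk. A t-test on fractions would reject too often in the upward direction under no effect. A ranking by mean fraction could favour metrics that rise over metrics that fall. If harm shows as higher stiffness and lower reactivity (an inference, since the documents state no direction), stiffness would gain an artificial advantage.

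A smaller worry concerns the blood markers. The plan looks at distributions first but does not say what that look can change, and raw-scale tests lose power if change and error are proportional to level.

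**Working it through.** **Inputs.** From the plan: paired test, two-sided, 0.05 for each parameter, one exam before and one after. Assumed, because the documents give none: measurement CV c of 5 to 30%, n of 10 to 100, correlation rho between the two exams' errors of 0 to 0.8, and between-subject log-SD of 0.25 (0.3 for the ranking figures). The plan states no figure to reproduce.

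**Bias of a mean of individual fractions.** Let pre = T(1+e1) and post = T(1+d)(1+e2), where T is the subject's true baseline, d the true change and e1, e2 the measurement errors. Then

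E[(post−pre)/pre] − d ≈ (1+d)·c²·(1−rho).

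- No true change, rho 0: 0.05² = 0.0025, 0.10² = 0.010 and 0.20² = 0.040, that is +0.25, +1.0 and +4.0 points.
- True 10% fall, c = 20%, rho 0: 0.9 × 0.04 = 0.036, so the mean fraction reads −6.4%.
- True 10% rise, c = 20%, rho 0: 1.1 × 0.04 = 0.044, so it reads +14.4%.
- No true change, c = 20%: rho 0.5 gives 0.04 × 0.5 = 2.0 points, and rho 0.8 gives 0.04 × 0.2 = 0.8 points.

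Simulation with lognormal error agrees with these values. The ratio of means and the mean log ratio show no such bias at any CV tried.

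**Type I error (20,000 simulated trials per setting, independent errors).**

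| n | CV | t-test on fractions | t-test on pre/post values |
|---|---|---|---|
| 10 | 20% | 5.2% | 4.7% |
| 20 | 20% | 6.5% | 4.8% |
| 30 | 5% | 5.2% | 5.1% |
| 30 | 20% | 8.4% | 4.7% |
| 50 | 20% | 13.1% | 4.8% |
| 100 | 20% | 24.3% | 5.0% |

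Over all settings tried (n 10 to 100, CV 5 to 30%), the test on pre and post values stayed between 4.5 and 5.2%. At n = 30 and CV 20%, the fraction test falls from 8.4% to 5.7% if rho is 0.8.

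**Which column is the plan's?** A paired t-test takes two values per subject, and the sentence applies it to each parameter. A test of fractions would be a one-sample test of a derived variable. The sentence on fractional change says only that it will be determined, which fits a descriptive summary. The right-hand column is therefore the natural reading.

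**Ranking.** Take a 10% fall measured with CV 5% and a 12% fall measured with CV 20%, at n = 30. Ranking by mean fraction puts the 10% fall first in 60% of trials, against 35% by ratio of means. That counts as an error only if sensitivity means the largest true percent change. If it means detectability, noise should count against a metric: change over CV is 0.10/0.05 = 2.0 for the first and 0.12/0.20 = 0.6 for the second. Ranked by the size of the paired t, the first metric leads in 99.9% of simulated trials. The sensitivity sentence directly follows the t-tests, and t and p are unit-free too, so a mean of fractions is not needed to compare metrics.

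**Blood markers.** At between-subject log-SD 0.5, if error is proportional and the log ratio has 80% power, the raw test has 67 to 71%. If error is additive and the raw test has 80%, the log ratio has 69 to 71%. The loss is about the same either way, and the documents do not say which error model holds.

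**The case for a change.** The strongest case for a change is that identifying the most sensitive metric is a stated purpose, yet its criterion is open and could be settled after the data are seen. Fractional change is the measure the plan names for qMRI, each fraction rests on one baseline exam, and the remedy is a few words. If mean fractions did decide the ranking, the effect could be large. With true changes of +10% and −10%, equal CV of 20%, n = 30 and independent errors, the rising metric would rank first in 85% of trials, when neither should be favoured.

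The omission stands, and so does the algebra. The inference that the planned analysis is biased does not. The large figures need several assumptions at once: individual fractions used for ranking or testing, CV near 20%, and errors unrelated between two exams in the same visit. Some shared error is plausible there, although the documents give no value for it.

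Nor is any single scale neutral. Under lognormal error, ranking +10% against −10% by raw paired t at equal CV and n = 30 puts the riser first in only 37 to 45% of trials, so prescribing one statistic would exchange one modest asymmetry for another. The regression on within-subject changes also leaves its scale open, but it is a supplementary step and the named paired tests do not depend on it.

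**Conclusion.** No change to the plan follows. On the natural reading the qMRI tests compare pre with post values and hold their nominal error rate (4.5 to 5.2% across the settings tried). The denominator bias belongs to an analysis that the plan does not state. Even there, with no true change it is 0.25 points at CV 5%, and at CV 20% between 0.8 points (rho 0.8) and 4 points (rho 0). Every CV, n, SD and correlation here is assumed.

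The unstated scale and ranking criterion are missing detail that a competent analyst fills by testing pre and post values, using percent change as description, and saying in the report what sensitivity was taken to mean. A reader of the results should check that individual fractions were not averaged to rank the metrics. For the blood markers, raw against log scale is a fair trade-off: the raw paired t-test is valid, and moving to logs gains about as much power under one error model as it loses under the other.

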### Analyses

Descriptive statistics will initially be performed to determine the characteristics of the various distributions and to identify outliers by displaying the data in the form of box and whisker plots and by computing means and standard deviations. Acute changes from baseline (blood draws pre- and post e-cig aerosol challenge) will be evaluated by paired t-tests for each of the variables listed above. To compare the qMRI metrics with inflammatory indices, Spearman correlations will be performed. We expect moderate inter-modality correlations ( $R^2 \sim 0.5$ ) for individual qMRI measures. We then use linear regression to create a classification model using the eight qMRI indices jointly. We expect  $R^2 > 80\%$ , substantially greater than each individual parameter alone, indicating that inhaled e-cig aerosol promotes *systemic EDF*.

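### Should the biomarker paired t-tests be moved to a log scale, with a rule for switching back?

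*Combined protocol and SAP*

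**What the plan says.** All references are to the combined protocol and SAP.

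- **Assays.** Data and Statistical Analysis names seven analytes (MCP-1, MIP-1, sICAM, sRAGE, IFN-γ, TNF-α, HMGB1): "Inflammatory biomarkers will be detected via enzyme-linked immunosorbent assay (ELISA) techniques from blood draws #1 and 2".
- **Order of work.** Analyses begins with a look at the data: "Descriptive statistics will initially be performed to determine the characteristics of the various distributions and to identify outliers". Box plots, means and SDs are the tools. Acute changes from baseline then "will be evaluated by paired t-tests for each of the variables listed above". The text does not say raw, log or percent.
- **Link to imaging.** "To compare the qMRI metrics with inflammatory indices, Spearman correlations will be performed". It does not say whether levels or changes are correlated.
- **Imaging metrics.** Data and Statistical Analysis states: "The fractional changes in functional and mechanical qMRI parameters between pre- and post-nicotine challenge will be determined". The section then says that, for all of these metrics at the 0.05 level, "paired two-tailed t-tests will be performed". It adds: "The data will allow us to determine which of the qMRI metrics" respond most to the aerosol, without giving a criterion.

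No sample size, power, SD, CV or expected biomarker change appears anywhere.

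**The concern.** Read plainly, the plan tests differences in raw concentration. If levels are right-skewed and measurement error grows with level, a few subjects with high concentrations dominate the variance of those differences, and a real change may be missed. A log ratio removes that dependence and needs no new samples. The plan also looks at distributions first but says nothing about what follows, so the choice of scale could be made after results are seen.

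Three smaller points come with it. The scale of change would alter Spearman ranks if changes are correlated. A fractional change averaged per subject as (post − pre)/pre is biased upward. And the imaging metric most responsive to the aerosol is to be picked without a stated yardstick.

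The remedy considered here has these parts:
- a paired t-test on log ratios by default, switching an assay to raw differences if the size of the change is less strongly associated with level on the raw scale than on the log scale;
- a Wilcoxon test on log ratios for any assay with non-detects;
- percent change from logs for the imaging metrics.

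**Working it through.** **Inputs.** From the documents: seven assays, two paired draws, paired t-tests, two-sided 0.05 (stated for imaging, assumed for the biomarkers). The plan states no power figure to reproduce. Assumed: n = 15, 30, 60; true ratio 1.25; per-reading log SD 0.3; between-subject log SD b from 0.2 to 1.0.

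**1. Log test under proportional error, n=30.** The SD of a log ratio is 0.3 × √2 = 0.424. The standardized effect is ln(1.25)/0.424 = 0.223/0.424 = 0.526. Noncentrality is 0.526 × √30 = 2.88. Exact noncentral-t power is 79.5%, whatever b is.

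**2. Raw test against the switching rule, same model** (30,000-40,000 simulated trials per setting):

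| n | raw, b=0.2 | b=0.5 | b=0.8 | b=1.0 | switching rule |
|---|---|---|---|---|---|
| 15 | 45% | 39% | 30% | 24% | 47% |
| 30 | 76% | 69% | 57% | 48% | 79% |
| 60 | 97% | 93% | 84% | 75% | 98% |

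Independent reruns agree to within about a point. A second set of assumptions (15% rise, within-subject log SD 0.2, n=30, b = 0.2, 0.4, 0.7, 1.0) gives raw 72%, 67%, 56%, 44% against 74-75%. The gain is 2-3 points with little spread and about 30 with wide spread.

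Over seven assays that all truly rise 25%, the expected detections at n=30 are:
- b=0.8: 7 × 0.565 = 4.0 raw against 7 × 0.786 = 5.5 with the rule;
- b=0.2: 7 × 0.762 = 5.3 against 7 × 0.791 = 5.5.

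**3. Validity of the raw test.** Type I error at n=30 under the proportional model is 3.5-4.8%. The raw test is slightly conservative, so a significant result can be trusted.

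**4. Where logs lose, n=30.**

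- *Additive error and effect, raw power set to 80%.* Logs alone give 78%, 71%, 58%, 50% at b = 0.2, 0.5, 0.8, 1.0. The switch restores 79-80%.
- *Response that differs between subjects.* The switch does not help:

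| Response pattern | raw | switching rule |
|---|---|---|
| Individual log response with SD 0.3, b=0.2 | 71% | 63% |
| 30% of subjects double, the rest unchanged, b=0.2 | 64% | 55% |
| Only subjects above the median level respond (×1.4), b=0.2 to 0.8 | 60-65% | about 50% |

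The check reverted to raw in only 0.2-4% of such trials, because it looks at spread against level and not at where the effect lies. The pattern is not one-sided: with random responders the two tie at b=0.5, and the rule wins at b=0.8 (54% against 42%).

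- *Non-detects under additive error, 10% of baselines below the limit.* The forced Wilcoxon test on log ratios gives 72%, 70%, 66% at b = 0.5, 0.8, 1.0, against 76%, 77%, 75% for the raw t-test with values set to the limit.

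**5. The smaller points.**

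- *Spearman on changes, n=30.* If the imaging change correlates 0.7 with the biomarker log ratio (the Analyses section expects R² near 0.5), mean rho is 0.67 on log ratios and 0.65, 0.62, 0.59, 0.57 on absolute differences at b = 0.2, 0.5, 0.8, 1.0. This is again under the proportional model.
- *Fractional change.* With no true change, the mean of (post − pre)/pre is exp(s²) − 1, where s² = ln(1 + CV²), so the bias equals CV². At CV 5%, 10%, 20% that is +0.25%, +1%, +4%. As a ratio of means at n=30 it is below 0.2%. Paired t-tests on the pre and post values are not biased. Pairing those raw tests with a log-based interval would make p-value and interval disagree on significance in about 10% of trials at CV 20%, a true 10% fall and between-subject log SD 0.3.
- *Ranking the imaging metrics.* The standardized change is d = mean change/SD of change, and the paired statistic is t = d√n. At a common n, d and t rank the metrics identically, so the planned tests already supply the yardstick.

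**The case for a change.** The strongest case for acting is that the plan is silent on scale, the two draws are fixed, and the analysis scale is one of the few levers that cost nothing. Under proportional error the gain may reach 30 points. The switching rule ignores p-values and held type I error at 4.6-5.3% in its own null settings (up to 5.6% for a close variant). Silence also leaves room for choosing the scale after seeing results: picking the smaller of the two p-values gave type I error between 5.6% and 7.8%.

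Part of this stands. The scale is unspecified, the distribution check leads to no stated action, and one sentence naming a scale would do no harm. The claim of a cheap gain does not stand. It depends on proportional error, wide between-subject spread and a fairly uniform response, and the documents establish none of these. The switch protects against additive error but not against uneven response. The log test also targets a geometric rather than an arithmetic mean, so the two scales answer somewhat different questions. Calling the planned tests untransformed is itself an inference from silence, although it is the natural reading.

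**Conclusion.** No change is called for. As written, the plan gives valid tests, with a planned look at distributions and outliers from which a competent analyst would choose and report a scale. The possible effect of moving to logs at n=30 runs from a gain of about 30 points of power (proportional error, wide spread) through about 3 points (little spread) to losses of roughly 8-15 points (uneven response) or 30 points (additive error, wide spread, no switch). All of these rest on assumed sample sizes, SDs and response models, and the documents do not show which applies. Statisticians could reasonably differ on the scale, and more so on a data-driven switch. The Spearman inputs, the definition of fractional change and the criterion for comparing imaging metrics are unspecified details of small consequence. Naming the biomarker scale in advance would be an optional clarification and would not correct an error.
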